**Table 5 infigratinib dose reductions**

Dose Adjustment	Oral Dose	Frequency
0	125 mg	QD
-1	100 mg	QD
-2	75 mg	QD

A Phase 0 Study of Infigratinib in Recurrent Glioblastoma Patients  
Protocol 2020-08

If a participant receiving the 75-mg dose of infigratinib requires further dose reduction, infigratinib should be discontinued. Based on the judgment of the investigator, if a participant is receiving clinical benefit from study therapy and requires further dose reduction than what is outlined in the table above, the investigator must discuss with the IBTC Safety Officer prior to further dose reduction.

Dose omissions are allowed within a cycle. If a participant requires omission of more than 25% of doses during a cycle for tolerability, then treatment may continue if the investigator determines the participant is receiving clinical benefit.

To ensure patient safety the investigator should collect specific recommended clinical information and follow-up laboratory tests as shown below in [Table 6](#).

Details for hepatic monitoring depend upon the severity and persistence of observed laboratory test abnormalities. If a study patient experiences elevated ALT 5×ULN and elevated TBL 2×ULN, or ALT 8×ULN, liver tests, including ALT, AST, TBL, direct bilirubin, gamma-glutamyl transferase (GGT), and creatine phosphokinase (CPK), should be repeated within 3 to 5 days to confirm the abnormality and to determine if it is increasing or decreasing. If the abnormality persists or worsens, clinical and laboratory monitoring should be initiated by the investigator, based on the hepatic monitoring tests below.

**Table 6 Hepatic Monitoring Tests for a Hepatic Treatment Emergent Abnormality**

Hepatic Hematology	Haptoglobin
Hemoglobin	
Hematocrit	Hepatic Coagulation
RBC	Prothrombin Time
WBC	Prothrombin Time, INR
Neutrophils, segmented and bands	
Lymphocytes	Hepatic Serologiesa
Monocytes	Hepatitis A antibody, total
Eosinophils	Hepatitis A antibody, IgM
Basophils	Hepatitis B surface antigen
Platelets	Hepatitis B surface antibody
	Hepatitis B Core antibody
Hepatic Chemistry	Hepatitis C antibody
Total bilirubin (TBL)	Hepatitis E antibody, IgG
Direct bilirubin	Hepatitis E antibody, IgM
Alkaline phosphatase	
ALT	Anti-nuclear antibody
AST	Anti-actin antibody
GGT	Anti-smooth muscle antibody
CPK	

A Phase 0 Study of Infigratinib in Recurrent Glioblastoma Patients  
Protocol 2020-08

Abbreviations: ALT = alanine aminotransferase; AST = aspartate aminotransferase; CPK = creatine phosphokinase; GGT = gamma-glutamyl transferase; Ig = immunoglobulin; INR = international normalized ratio; RBC = red blood cells; WBC = white blood cells.

a Reflex/confirmation dependent on regulatory requirements and/or testing availability.

## 6.2 PREPARATION/HANDLING/STORAGE/ACCOUNTABILITY

### 6.2.1 ACQUISITION AND ACCOUNTABILITY

Infigratinib will be provided by QED to IBTC and will be labeled according to regulatory requirements. QED will distribute to the investigative sites.

### 6.2.2 FORMULATION, APPEARANCE, PACKAGING, AND LABELING

QED will perform the labeling and the final packaging of these study medications under good manufacturing practice (GMP) conditions.

### 6.2.3 PRODUCT STORAGE AND STABILITY

Infigratinib will be supplied as 100-mg and 25-mg capsules for oral consumption. Infigratinib hard gelatin capsules are packaged in white HDPE (high-density polyethylene) bottles with aluminum induction seal and child-resistant screw cap closure. Please refer to clinical labels for current shelf-life, in-use period and storage conditions for infigratinib hard gelatin capsules.

Investigators should instruct participants to store the capsules at home in the original container and to keep out of the reach of children. Capsules should not be opened, crushed, or dissolved.

### 6.2.4 DISPOSAL AND DESTRUCTION

The study drug supply can be destroyed at the institution or third party, as appropriate, if permitted by local regulations, policies and authorized by IBTC.

## 6.3 STUDY INTERVENTION COMPLIANCE

Participant compliance with study medication will be assessed at each visit. Compliance will be assessed by direct questioning, review of the dosing diary and counting returned capsules. In the Expansion Cohort, plasma levels will be measured for the first 2 cycles on days 1, 8, and 15. Deviations from the prescribed dosage regimen should be recorded in the CRF. A participant dosing diary will be used to capture dose information for infigratinib for in clinic and at home dosing.

The participant must take  $\geq 80\%$  of the intended doses in each cycle to be deemed compliant with study drug administration. Similarly, a participant may be considered noncompliant if he or she is judged by the investigator to have intentionally or repeatedly taken more than the prescribed amount of drug(s). Potential discontinuation of a participant due to study drug noncompliance will be discussed between the investigator and IBTC before the final determination is made to discontinue the participant.

## 6.4 CONCOMITANT THERAPY

## A Phase 0 Study of Infigratinib in Recurrent Glioblastoma Patients Protocol 2020-08

For this protocol, a prescription medication is defined as a medication that can be prescribed only by a properly authorized/licensed clinician. Medications to be reported in the Case Report Form (CRF) are concomitant prescription medications, over-the-counter medications and supplements.

No other chemotherapy, radiotherapy immunotherapy, cancer related hormone therapy, or experimental drugs, or herbal supplements intended to treat cancer will be permitted while the participants are on this study. An exception will be made for the following circumstances:

- prostate cancer participants continuing GnRH agonist therapy or breast cancer participants continuing antiestrogen therapy (for example, an aromatase inhibitor).
- palliative radiotherapy of ≤14 calendar days in Cycles 2 and beyond following discussion and approved in writing by the IBTC (e.g., for a solitary skeletal metastasis), as long as the participant has not developed another reason for study discontinuation
- in select cases, after discussion and approved in writing by IBTC, local therapies (such as radiation treatment to control isolated areas of CNS progression) may be permissible after cycle 1 provided study drug(s) are held on the days of local therapy.

In addition, any disease progression requiring other forms of specific antitumor therapy will also necessitate early discontinuation from the study. Replacement hormone therapy initiated before study entry will be allowed.

For the craniotomy in Phase 0, anesthesia may use medications that would otherwise be prohibited when deemed clinically necessary, but if possible, should be avoided.

Investigational agents used to improve surgical resection, craniotomy, wound healing, or recovery are allowed.

All concomitant medication and concurrent therapies administered within 30 days of study entry will be documented at Screening and during the study. Dose, route, unit frequency of administration, and indication for administration and dates of medication will be captured.

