#### 4.1.2 EXPANSION COHORT DESIGN

Participants with tumors demonstrating PK-response in Phase 0 will continue treatment with the same dose continuously for 21 days in 28d cycles after surgery. This will constitute the Expansion Cohort component of the study. PD biomarkers will be included for exploratory analyses. Expansion Cohort participants will be contacted every 3 months by letter or phone for collection of survival data.

Participants will be treated until unacceptable toxicity is observed, or until disease progression as assessed by RANO criteria.

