#### 6.1.2 DOSING AND ADMINISTRATION

In Phase 0, the dose for infigratinib will be 125 mg oral (PO), taken QD over 7 days on Day 1 through Day 7. The last dose will be given on the morning of Day 7, approximately 7-9 hours prior to craniotomy for tumor resection. Day 1 and Day 7 doses will be taken in the clinic. Days 2-5 will be taken at home. Day 6 will be taken at home or in clinic (Table 2).

**Table 2** Phase 0 Dose Schedule

Study Intervention	infigratinib
Day 1	125 mg In Clinic
Day 2	125 mg At Home
Day 3	125 mg At Home
Day 4	125 mg At Home
Day 5	125 mg At Home
Day 6	125 mg At Home or Clinic
Day 7	125 mg In Clinic

In the Expansion Cohort, the dose for infigratinib will be 125 mg oral (PO) QD on Days 1 through 21 in a 28-day cycle. On days with a trough PK sample, the doses will be administered in clinic, if possible (Cycle 1 & 2, Days 1, 8, and 15). A delay of a cycle due to holiday, weekend, bad weather, or other unforeseen

A Phase 0 Study of Infigratinib in Recurrent Glioblastoma Patients  
Protocol 2020-08

circumstances will be permitted for a maximum of 7 days and not counted as a protocol deviation. The reason for the treatment interruption should be documented on the CRF. A cycle begins when study treatment is dispensed for the cycle and administered. Thus, if an expected cycle start is delayed, the number of days in the current cycle is increased beyond 28 days. A visit window of  $\pm 1$  day in Cycle 1 and 2 on Days 1, 8, and 15 and  $\pm 3$  days in Cycle 3 onward is allowed.

A participant may continue to receive study treatment until confirmed progressive disease, unacceptable toxicity, or discontinuation for any other reason.

Participants should be instructed to take the daily dose of infigratinib in the morning in a fasted state at least at least 1 hour before or 2 hours after a meal. Infigratinib should be taken at approximately the same time each day (24  $\pm$  2 hours interval). Subjects should be instructed to swallow the capsules whole, i.e., without chewing, with a glass of water (~250 mL), which should be consumed over as short a time as possible.

If vomiting occurs after ingestion of a daily dose, no re-dosing of the participant should occur before the next scheduled dose. Also, if a dose cannot be administered early in the day, that dose should not be made up later that day, and dosing should resume the following day.

---

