#### 6.4.1.2 PROHIBITED CONCOMITANT THERAPY

A concomitant medication is considered prohibited if it appears on any of the prohibited medication lists for any clinical pharmacology property of the drug (eg, CYP, BCRP).

Details for specific medications prohibited while on study are provided in [Table 8](#). The rationale for the restricted medications is provided below.

Other investigational therapies must not be used while the participant is on the study. Anticancer therapy (chemotherapy, biologic or radiation therapy, and surgery) other than the study drug must not be given to participants while the participant is on study drug. If such agents are required, then the participant must be discontinued from study drug. The only exception is palliative localized radiation therapy for bone metastases with approval by QED Therapeutics' medical monitor.

Strong inhibitors of CYP3A4 such as the ones listed in [Table 8](#) are prohibited because infigratinib is a likely substrate of this isoenzyme.

Strong inducers of CYP3A4 are prohibited because their usage may decrease the exposure of infigratinib. Therefore, agents such as those listed in [Table 8](#) are prohibited. Please note that the list may not be exhaustive.

Subjects must also avoid the consumption of grapefruits, grapefruit juice, grapefruit hybrids, pomegranates, star fruits, pomelos, Seville oranges or juice within 7 days prior to the first dose of infigratinib and throughout the treatment period due to a potential CYP3A4 interaction with study drug.

Medications that increase the serum levels of phosphorus and/or calcium are prohibited.

A Phase 0 Study of Infigratinib in Recurrent Glioblastoma Patients  
Protocol 2020-08

prolong the QT/QTc interval or induce TdP (risk of TdP/QT prolongation) are prohibited. List of these medications is given in [Table 8](#). Please note that the list might not be comprehensive.

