## 7 STUDY INTERVENTION DISCONTINUATION AND PARTICIPANT DISCONTINUATION / WITHDRAWAL

### 7.1 DISCONTINUATION OF STUDY INTERVENTION

Discontinuation from treatment does not mean discontinuation from the study, and remaining study procedures should be completed as indicated by the study protocol. If a clinically significant finding is identified (including, but not limited to changes from baseline) after enrollment, the investigator or qualified designee will determine if any change in participant management is needed. Any new clinically relevant finding will be reported as an adverse event (AE).

The data to be collected at the time of study intervention discontinuation will include the end-of-study (EOS) procedures as shown in Section 1.2.

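### Sections 6.4 and 6.4.1.2 give opposite drug rules for a participant irradiated for isolated CNS progression, and 9.4.1 counts tumour control by radiation given before RANO progression as a PFS6 success

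*Combined protocol and SAP*

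**What the plan says.** **Section 6.4 (Concomitant Therapy)** bars other anticancer treatment on study and then lists exceptions. One is that "local therapies (such as radiation treatment to control isolated areas of CNS progression) may be permissible after cycle 1", in select cases, after discussion and written IBTC approval, "provided study drug(s) are held on the days of local therapy". The section goes on to say that progression needing other kinds of antitumour therapy means leaving the study early.

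**Section 6.4.1.2 (Prohibited Concomitant Therapy)** bars radiation, among other anticancer treatments, while a participant is on study drug. It continues: "If such agents are required, then the participant must be discontinued from study drug". It then closes its own list: "The only exception is palliative localized radiation therapy for bone metastases with approval by QED" (the drug supplier's medical monitor).

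**Sections 4.1.2 and 6.1.2** set the end of Expansion treatment. Apart from toxicity, 4.1.2 treats "until disease progression as assessed by RANO criteria". Section 6.1.2 says: "A participant may continue to receive study treatment until confirmed progressive disease, unacceptable toxicity, or discontinuation for any other reason".

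**Section 9.4.1** runs PFS from surgery to first documented progression (per RANO) or death. It has one censoring rule: the last tumour assessment, for those alive without progression. It has one event rule outside RANO: removal from treatment for symptomatic deterioration. It does not mention radiation or any other new anticancer therapy. Section 9.1 says there will be no separate SAP, and the data handling rules in 9.4.5 add nothing on this.

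**The concern.** The protocol gives two answers to a practical question: does a participant who needs CNS radiation stay on infigratinib? Section 6.4 says yes, with a pause on the therapy days. Section 6.4.1.2 says no, and because it names a single exception it cannot be read as a general rule that yields to 6.4.

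The answer can also change the primary endpoint of the Expansion Cohort. A participant kept on drug under 6.4 is not removed for symptomatic deterioration, so the one non-RANO event rule in 9.4.1 does not apply. If radiation then holds the tumour and RANO progression is not reached by 6 months, that participant is progression-free in a single-arm result that will be read as the effect of infigratinib.

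**Working it through.** **1. The drug rules for one participant, after cycle 1, with isolated CNS growth for which radiation is wanted**

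| Section | Radiation | Infigratinib |
|---|---|---|
| 6.4 | allowed in select cases with written IBTC approval | held on therapy days, then resumed |
| 6.4.1.2 | not allowed on drug; bone metastases are the sole exception | discontinued |
| 4.1.2, 6.1.2 | not addressed | ends at RANO or confirmed progression |

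No section reconciles the first two rows.

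**2. What this does to PFS6 depends on what progression means in the 6.4 bullet**

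- *It already meets RANO.* Section 9.4.1 dates an event, so PFS6 is unaffected. What remains is the conflict over continuing drug.
- *It falls short of RANO, or RANO progression has not been documented* (for example an enhancing increase below the 25% threshold in 8.1.4.1). There is no event. On the 6.4 route drug continues, and a participant then controlled by radiation is progression-free at 6 months. On the 6.4.1.2 route drug stops. Section 7.1 says "remaining study procedures should be completed as indicated by the study protocol", and the Schedule of Activities has an end-of-treatment MRI and RANO assessment but lists no MRI after it. The same participant could then be an event, a success or censored.

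**3. Can the second situation arise?** Section 6.4 does not require a RANO assessment before the radiation. The exception opens after cycle 1 (28 days), and RANO is scheduled every 3 months. With the 9.4.5 conversion, 3 × 30.4375 = 91.3 days.

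- Interval counted from Expansion day 1: 91.3 − 28 = 63.3 days open before the first scheduled on-treatment assessment.
- Interval counted from surgery, with Expansion assumed to start 14 to 42 days later: 91.3 − (14 + 28) = 49.3 days, down to 91.3 − (42 + 28) = 21.3 days.

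This shows that the case is possible. It is not a probability of use.

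**4. Cohort size.** Section 9.2 gives 400 patients per year, 5% with the alteration, 50% capture, 24 months, and half entering Expansion:

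- 400 × 0.05 = 20 eligible per year; 20 × 0.50 = 10 enrolled per year; 10 × 2 = 20, the plan's figure.
- 20 × 0.50 = 10 in Expansion.

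One participant is therefore 1/10 = 10 points of PFS6. If Expansion were 5 it would be 1/5 = 20 points; if all 20 entered, 1/20 = 5 points.

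**5. Illustration at n = 10.** The outcome splits are assumed; the documents give none. Intervals are exact (Clopper-Pearson) at the 80% level of 9.1. The censored figures assume Kaplan-Meier, because 9.4.1 names no PFS estimator and 9.4.6 names Kaplan-Meier for OS only.

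| Assumed outcomes | 9.4.1 as written | Counted as event | Censored |
|---|---|---|---|
| 7 progress, 2 event-free, 1 irradiated before RANO progression and then controlled | 3/10 = 30% (11.6 to 55.2) | 2/10 = 20% (5.5 to 45.0) | 22.2% to 30.0% |
| 6 progress, 2 event-free, 2 irradiated before RANO progression and then controlled | 4/10 = 40% (18.8 to 64.6) | 2/10 = 20% (5.5 to 45.0) | 25.0% to 40.0% |

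The censored range runs from censoring before every progression (2/9 = 22.2%; 2/8 = 25.0%) to censoring after every progression (3/10; 4/10).

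**The case against.** **The carve-out may be deliberate.** Section 7.2 lists progression that requires stopping drug as a reason an investigator may discontinue a participant, which leaves room for progression that does not. The sentence in 6.4 about other forms of antitumour therapy also fits a planned exception. On that view 6.4.1.2 merely lacks a cross-reference. This stands as an account of intent, so it goes too far to say that the bullet cannot be made coherent. It does not remove the conflict, because 6.4.1.2 states that it has only one exception.

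**Sites cannot act on their own.** A reader might infer that sites could treat the same participant in opposite ways, each citing the protocol. The documents do not support that for the 6.4 route: IBTC must approve each use in writing.

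**The RANO definition is broad.** Section 8.1.4.1 counts any new lesion, a 25% increase, a significant T2/FLAIR increase or clear clinical deterioration. Growth judged to need radiation will often meet one of these. Section 9.4.1 does not limit documentation to scheduled scans, and MRI is routine care. This stands, and it makes the endpoint problem uncommon.

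**Section 9.4.1 has a working default.** Following PFS through radiation is a legitimate estimand in a study with no formal hypotheses. But the plan does not say that it chose this, and the result would be read as drug effect.

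**The approvers differ.** For palliative radiotherapy 6.4 says "in Cycles 2 and beyond following discussion and approved in writing by the IBTC", while 6.4.1.2 names the supplier's medical monitor. A reader might call this a second contradiction. It is minor: both approvals can apply, and it concerns bone or skeletal metastases.

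**Conclusion.** The conflict between 6.4 and 6.4.1.2 is an error as written. It decides who stays on infigratinib, and it stands even if no participant is ever irradiated before RANO progression.

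The effect on PFS6 is real but conditional. It needs radiation before RANO progression is documented, followed by no RANO progression up to 6 months. Each such participant moves PFS6 by up to 10 points at the expected n of 10 (5 to 20 points for n of 20 down to 5). The number of select cases is not given and may be 0.

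A reader might infer that the PFS6 result would be materially biased. The documents do not support that. The 80% intervals in the illustration overlap widely, the splits are assumed, and PFS6 is descriptive under 9.1. The reason to act is that the change is cheap and that the rule should be set before outcomes are known.

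**What to change.** 1. **Section 6.4.** Delete the CNS local-therapy bullet, so that 6.4 agrees with 6.4.1.2, 4.1.2 and 6.1.2. A participant who needs CNS radiation then comes off drug and stays in follow-up. If the sponsor wants to keep the option, list it as an exception in 6.4.1.2 and require a RANO assessment before the radiation. If drug is to continue after RANO progression, 4.1.2 and 6.1.2 need a matching clause.
2. **Section 9.4.1.** Add: *Radiation or other local or systemic therapy given for growth or suspected progression of the glioma before RANO progression is documented counts as a PFS6 event on its start date.* Add a Kaplan-Meier sensitivity result that censors these participants at the last tumour assessment before that therapy.
3. **Limit the event rule.** Do not apply it to participants who stop for toxicity and start other therapy without progression. Table 3 has many mandatory toxicity stops, and a rule covering every new anticancer therapy would turn these participants into PFS6 failures. Handle them in the sensitivity analysis only.
4. **Data.** Use the therapy dates that 6.4 already requires on study. Ask for the start date of any new anticancer therapy at the existing post-treatment contacts.

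Cost: one bullet deleted or one exception added, a few sentences in 9.4.1, and one question at contacts already scheduled. The 3-monthly contact now collects survival only. No visits or scans are added. The downside is that PFS6 may be slightly lower, and a rarely used clinical option is removed or made conditional on a RANO assessment.

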### 6.4.1.1 PERMITTED CONCOMITANT THERAPY REQUIRING CAUTION AND/OR ACTION

Details for specific medications which require action and/or caution while on study in participants taking infigratinib are provided in [Table 7](#). The rationale for these medications is provided below.

Infigratinib is characterized by pH-dependent solubility, and therefore, medicinal products that alter the pH of the upper GI tract may alter the solubility of infigratinib, and limit bioavailability. These agents include, but are not limited to, proton pump inhibitors (e.g., omeprazole), H2-antagonists (e.g., ranitidine) and antacids. If possible, proton pump inhibitors should be avoided due to their long PD effect and replaced with H2-antagonists or antacids. Study drug should be taken ≥2 hours before or 10 hours after dosing with a gastric protection agent.

[figure not shown]
Infigratinib is a substrate of CYP3A4. Therefore, moderate inhibitors and inducers should be used with caution if an alternative is not available. If anticoagulation is required, heparin and/or low-molecular-weight heparins or direct thrombin inhibitors and/or Factor Xa inhibitors that are not metabolized by CYP3A4 (e.g., dabigatran, edoxaban) are preferred. If unavoidable, anticoagulants that are CYP3A4 substrates and have a narrow therapeutic index (e.g., warfarin sodium or any other coumadin-derivative anticoagulants or certain direct thrombin inhibitors [e.g., argatroban] or Factor Xa inhibitors [e.g., rivaroxaban]) should be used with caution.

A Phase 0 Study of Infigratinib in Recurrent Glioblastoma Patients  
Protocol 2020-08

Infigratinib was shown in vitro to inhibit the drug transporter breast cancer resistance protein (BCRP), with an IC50 of 210 nM. While the clinical relevance of this inhibition is unknown, drugs transported by BCRP should be used with caution.

Anti-emetics are recommended as clinically appropriate at the first sign of nausea and vomiting or as prophylaxis to prevent emesis, along with supportive care according to clinical practice guidelines.

It is recommended to avoid using drugs that are known to cause QT prolongation. Note that some anti-emetics have a known risk for Torsade de Pointes, and therefore need to be used with caution. See [Table 7](#) for list of drugs that need to be used with caution. Aprepitant (brand name: Emend) is both a sensitive substrate and a moderate CYP3A4 inhibitor and should be used with caution if an alternative is not available.

